Standard vs Ultrasound-assisted Catheter Thrombolysis for Submassive Pulmonary Embolism NCT03086317

Date: February 10, 2017 IRB number: 00093040

Standard vs Ultrasound-assisted Catheter Thrombolysis for Submassive Pulmonary Embolism

Principal Investigators: [name] and [name]

IRB number: 93040

Draft date: February 10, 2017

SUMMARY

Background: Acute pulmonary embolism (PE) accounts for 5-10% of in-hospital deaths. Systemic anticoagulation (AC) is the standard of care and thrombolysis is recommended for those at a higher mortality risk. Catheter-directed therapies mainly standard catheter thrombolysis (CDT) and ultrasound-accelerated thrombolysis (USAT) have been introduced as new more effective and safer treatment modalities. USAT is a modification of standard catheter lysis utilizing a system of local ultrasound to dissociate the fibrin matrix of the thrombus, allowing deeper penetration of lytics. However, there is limited comparative effectiveness data against standard multi-sidehole catheter infusion. More rapid clearance of pulmonary thrombus by USAT compared to standard CDT may prove to be clinically and cost effective. Alternatively, if thrombus clearance is similar, the cost of USAT may exceed the cost of CDT (equipment and disposables), without offering any potential advantage.

Hypothesis: Ultrasound Accelerated Thrombolysis is superior to Standard Catheter Thrombolysis for patients with submassive PE

Objectives/Aims: 1. Determine differences in the percentage of thrombus load reduction (CTA Obstruction Index) from baseline to the termination of lysis; 2. Determine differences in cardiopulmonary and clinical outcomes; **3.** Determine differences in the impact of catheter directed intervention on functional capacity (NYHA score and 6-min walk test) and health-related quality of life outcomes (SF36, PE QOL, and San Diego Shortness of Breath questionnaires at 3 and 12 months; 4. Detail the cost differences in hospital resource utilization (i.e., procedure costs, adverse event costs, and hospital stay) and discharge costs (nursing care, subsequent outpatient care) to inform a Markov state-transition cost-effectiveness model.

Design: Randomized controlled trial.

Statistical Power: The study is powered on the primary endpoint. 40 patients will be needed at each group for a power of 0.80.

RESEARCH PLAN

a. SPECIFIC AIMS

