- **Hypothesis:** Ultrasound Accelerated Thrombolysis is superior to Standard Catheter Thrombolysis for patients with submassive PE
- Aim 1: Determine differences in the percentage of thrombus load reduction from baseline to the termination of lysis between the two techniques
- Aim 2: Determine differences in cardiopulmonary (echocardiographic, hemodynamic and respiratory parameters) and clinical outcomes (decompensation, mortality, complications, ICU stay) between the two techniques
- **Aim 3:** Determine differences in the impact of catheter directed interventions on functional capacity and health-related quality of life outcomes at 3 and 12 months
- Aim 4: Perform a cost effectiveness analysis to compare quality adjust life years and costs of the two techniques.

b. BACKGROUND AND SIGNIFICANCE

Acute pulmonary embolism (PE) carries a high morbidity and is the third-leading cause of cardiovascular mortality in the western world. It accounts for 5-10% of in-hospital deaths that for the United States translates to 200,000 deaths per year.¹ Recent registries and cohort studies suggest that approximately 10% of all patients with acute PE die during the first 1 to 3 months after diagnosis.¹⁻⁵ Studies that have observed survivors for >3 months have reported an incidence of chronic thromboembolic pulmonary hypertension (CTEPH) 1-5% within 2-3 years after PE.⁶⁻¹⁰ It is an incapacitating long-term complication of thromboembolic disease with a negative impact on the patient's quality of life and prognosis.

The management acute PE is mainly guided by the acuity and severity of clinical presentation. Initial systemic anticoagulation (AC) is the standard of care and treatment is escalated based on the clinical presentation and patient characteristics that may stratify them at a higher mortality risk. The goals of therapy are to primarily prevent mortality, and secondarily potentially prevent late onset chronic thromboembolic pulmonary hypertension (CTEPH) and improve quality of life.^{2, 3, 5, 11-14}

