Limited data exists for comparing different catheter-directed therapies for acute PE. The majority of recent series for catheter-directed interventions utilize USAT exclusively; however there is limited comparative effectiveness data comparing this modality to standard multi-sidehole catheter infusion.^{15, 16, 19, 30} Preliminary, non-controlled data are conflicting. One series by Lin and colleagues of 33 high-risk PE patients suggested benefit for USAT for angiographic clearance of thrombus burden with more bleeding events in the CDT group.³¹ Kuo and colleagues noted no difference in outcomes and treatment specifics between USAT and CDT in the recently published early results of a multicenter prospective registry.²⁸ Our retrospective analysis of 63 patients suggests that there may be no difference between the two treatment modalities, demonstrating similar rates of outcomes such as survival, hemodynamic stabilization, and echocardiographic parameters in both groups with similar procedure length and lytic dose in the time-adjusted cohorts.³² Selection bias cannot be underestimated in all these studies.

The expected benefit of USAT has been dependent on the device's ability to increase penetration of lytic into thrombus using high frequency, low power ultrasound, due to its reversible effects on fibrin dissociation.^{19, 21} This benefit has been shown to result in faster thrombus clearance in selected vascular beds in some studies, such as the recently published DUET study comparing USAT and CDT in arterial occlusions.³³ Evidence from the venous circulation, coming

from the recent BERNUTIFUL trial demonstrated no difference in time to thrombus clearance in lower extremity deep venous thrombosis.³⁴

c. INNOVATION

There are no randomized controlled studies that have compared the outcomes of catheter directed thrombolysis with and without ultrasound acceleration. More rapid clearance of pulmonary thrombus by USAT compared to standard CDT may prove to be clinically and cost effective (e.g. via reduced length of ICU and hospital stay). Alternatively, if thrombus clearance is similar, the cost of USAT may exceed the cost of CDT (proprietary equipment and disposables), without offering any potential advantage.

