 - c. Major and minor bleeding. Major bleeding is defined as overt bleeding associated with a fall in the hemoglobin level of at least 2.0 g/dL or with transfusion of ≥2 U of red blood cells or involvement of a critical site (intracranial, intraspi-nal, intraocular, retroperitoneal, intra-articular or pericardial, or intra-muscular with compartment

syndrome). Clinically overt bleeding not fulfilling the criteria of major bleeding is classified as a minor bleeding complication.

- d. Recurrent venous thromboembolism (VTE) during 90-day follow-up. There will be no routine surveillance for asymptomatic recurrent VTE. Recurrent VTE will be diagnosed if suspected symptoms or signs of deep vein thrombosis or acute PE are objectively confirmed by an imaging test (new filling defect by pulmonary angiography or contrast-enhanced chest CT, new high-probability perfusion defect revealed by lung scan, or positive compression ultrasound study for deep vein thrombosis).
- e. Major adverse events up to 90 days after randomization.
- f. Clinical success: PE related decompensation prevention without a 90-day major adverse event or death.
- g. ICU length of stay
- 2. Echocardiographic parameters comparison
 - RV/LV, TAPSE (Tricuspid annular plane systolic excursion) and RVSP (Right Ventricular Systolic Pressure) improvement from baseline to the termination of lysis
 - b. RV/LV, TAPSE and RVSP at 90 days
 - c. RV/LV, TAPSE and RVSP at 12 months

The echocardiograms will be interpreted by 2 blinded independent cardiologists.

3. Functional status and quality of life

At the 3 and 12-month follow-up visit, patients will complete a written survey to assess the NYHA score and answer other questions about functional status. Patients will then perform a 6-minute walk test according to published guidelines.^{37,38}Transthoracic echocardiography will be also performed as described earlier.

Quality of life will be assessed at 3 and 12 months using SF36, PE QOL, and San Diego Shortness of Breath questionnaires.

4. Cost effectiveness analysis

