A Markov state-transition, cost effectiveness model will be created to simulate patient oriented outcomes assuming a societal perspective with a 12-month time horizon. All point estimates for model parameters will be determined from the prospectively collected data, as described above. Quality adjusted life years will be determined for each therapy based on survival, freedom from major adverse events, discharge status, functional status, and quality of life measures. Costs will be calculated for each therapy based on in-hospital resource utilization (i.e., length of stay in the ICU, operating room and procedure costs, and associated adverse event costs) and out-of-hospital costs (outpatient nursing care, loss of work, outpatient testing and follow-up).

Schedule of Events

			Randomization US assisted or standard		Prior to Lysis Termination	Within	3month f-up	12month f-up
	Deceline	Correction	catheter	Lysis	or within 24h	48hrs	+/-14	+/- 30
	Baseline	Screening	thrombolysis	Procedure	post lysis	post lysis	days	days
Informed Concept		V						
	X	X				N N		
Chest CTA	X					X		
Transthoracic								
Echocardiogram	X				X		X	X
Cardiac troponin	×							
Drain Natriuratia								+
Brain Natriuretic	v							
	^							
N-terminal pro-								
BNP(NI-proBNP)	X							
IV Unfractionated								
Heparin		X						-
Vital Signs		X						
2min Pulse Ox		X						
Ultrasound								
Catheter Placement			Х	Х				
Standard Catheter								
placement			X	X				
Invasive Pressure								
Tracings from drug								
delivery catheter				X(a)	X(b)			
Functional Status								
NYHA							X	X
Quality of Life								
Questionnaires							X	X
Six Minute Walk Test							x	x

(a) Before lytics administered

(b) After lytics administered

Statistical Analysis:

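### The two definitions of in-hospital cost conflict: the Summary counts hospital stay, the cost-effectiveness section counts ICU stay only, so routine ward days may go uncosted

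*Combined protocol and SAP*

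**What the plan says.** Inpatient stay is treated differently in different parts of the document.

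- **Summary, Objectives/Aims 4:** cost differences will be detailed for "hospital resource utilization (i.e., procedure costs, adverse event costs, and hospital stay", to inform the Markov model. Stay is not restricted to the ICU.
- **Section d, Secondary Endpoints 4 (Cost effectiveness analysis):** in-hospital cost is calculated from "in-hospital resource utilization (i.e., length of stay in the ICU, operating room and procedure costs, and associated adverse event costs". The other cost group is "out-of-hospital costs (outpatient nursing care, loss of work, outpatient testing and follow-up". The perspective is societal over 12 months, and model parameters are to come from the trial data described earlier in the plan.
- **Section c, Innovation:** USAT "may prove to be clinically and cost effective (e.g. via reduced length of ICU and hospital stay".
- **Section a, Aim 2, and Secondary Endpoint 1g:** the stay outcome is ICU stay only, given as "clinical outcomes (decompensation, mortality, complications, ICU stay" and "ICU length of stay".
- **Section a, Aim 4:** "Perform a cost effectiveness analysis to compare quality adjust life years and costs of the two techniques". No cost items are listed here.

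**The concern.** Two passages define the same quantity, both introduce their list with *i.e.*, and the lists differ on bed-days. The narrower list stands in the section an analyst would work from. Anyone following it would price ICU days and give ordinary ward days no price, although they are a direct medical cost under the stated societal perspective.

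The economic question is whether faster clot clearance repays the extra equipment cost of USAT. The Innovation section gives shorter ICU and hospital stay as its example of how that could happen. With ICU days alone in the model, only half of that example can be tested. With the choice left open, the definition could also be picked after the data have been seen.

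**Working it through.** The documents give no length of stay, unit price or cost formula, so there is no plan figure to reproduce. The check is a comparison of texts followed by a short piece of algebra.

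**Step 1. The two inpatient lists**

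| Item | Summary, objective 4 | Cost effectiveness analysis |
|---|---|---|
| Procedure | yes | yes, with operating room |
| Adverse events | yes | yes |
| ICU days | within hospital stay | yes |
| Routine non-ICU days | within hospital stay | not listed |

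**Step 2. Does another part of the plan supply ward days?**

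- The out-of-hospital list covers nursing after discharge, lost work, and outpatient tests and visits. Inpatient ward days do not fit there.
- Model inputs are to come from data described earlier. In the Research Plan, the only stay measure described is ICU stay (Aim 2 and endpoint 1g).
- The Schedule of Events has no row for hospital stay. It has none for ICU stay or costs either, so its silence adds little.
- Ward days caused by a complication could be captured as adverse event costs. Routine ward days could not.

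**Step 3. What the omission does to the cost difference**

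Let Δ be the USAT mean minus the CDT mean. I is ICU days, W is non-ICU inpatient days not already costed as adverse events, c_I and c_W are their prices per day, and R is all other costs.

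- With hospital stay counted: Δcost = ΔR + c_I·ΔI + c_W·ΔW
- With ICU stay only: Δcost = ΔR + c_I·ΔI
- Error (second minus first) = −c_W·ΔW

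**Step 4. Cases, per patient**

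| Case | ΔI | ΔW | Stay saving, full count | Stay saving, ICU only | Saving misstated by |
|---|---|---|---|---|---|
| Ward stay equal in both arms | −1 | 0 | c_I | c_I | 0 |
| ICU day becomes a ward day, same discharge | −1 | +1 | c_I − c_W | c_I | c_W too much |
| Same ICU stay, discharge one day earlier | 0 | −1 | c_W | 0 | c_W too little |

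The error can therefore favour either arm, and it vanishes when ΔW = 0.

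**The case against.** The strongest reply is that total stay is already a named cost item. Objective 4 lists it for the same model, and nothing says that the later list overrides the Summary. The two out-of-hospital lists differ too: the later one adds lost work. Loose drafting is therefore a better explanation than a decision to drop ward costs, and a societal perspective fits poorly with dropping them on purpose. This stands. A reader might infer that the plan excludes ward days outright, but the documents support only a conflict between two definitions, one of which leaves them out.

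A second reply is that the omission cancels if the arms have similar ward stays. This is also right. A reader might infer that the cost comparison is biased in any event, but that needs a between-arm difference in ward stay, and the documents give no evidence of one. The investigators' retrospective series of 63 patients suggested similar outcomes between techniques. As summarised in the protocol, it does not mention length of stay, so it settles nothing either way.

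A third reply is that earlier discharge would not go wholly unrecognised: ICU days are priced, and lost work is counted. That is true, but neither prices the ward bed-days saved.

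Finally, endpoint 1g agrees with Aim 2, so the list of clinical endpoints contradicts no aim. A cost input need not be an endpoint, since procedure costs are not one. This stands, and the point is confined to the cost inputs.

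**Conclusion.** The contradiction is real and should be resolved before costs are analysed. If the cost-effectiveness section is followed as written, the incremental cost per patient is off by the price of a ward day times the between-arm difference in mean routine ward days, in either direction. This assumes that ward days caused by complications are costed under adverse events and that no unstated rule adds the rest. The amount cannot be estimated from the documents, and any bed-day total would rest on an assumed difference.

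Two further readings go too far. Shorter hospital stay is not presented as the main route to cost benefit: it is introduced with *e.g.*, though it is the only example given. And the unrestricted hospital-stay item appears in objective 4 of the Summary, not in Aim 4 of the Research Plan, which names no cost components.

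The point touches one input to one secondary analysis. It does not affect the primary endpoint, the sample size or the safety assessment.

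**What to change.** In Secondary Endpoints 4, replace the ICU-only stay item with *total hospital length of stay, split into ICU and non-ICU days*. This agrees with objective 4 of the Summary and with the example in the Innovation section. Price the two kinds of day separately, and say that days attributed to an adverse event are counted once. Collect admission, ICU-transfer and discharge dates as cost inputs.

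The cost is one changed phrase, a little more data abstraction from dates that hospital records would normally hold, and one more unit cost. Endpoint 1g can stay as it is, and no clinical endpoint needs to be added.

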Preliminary, non-controlled data are conflicting. One series by Lin and colleagues of 33 highrisk PE patients suggested benefit for USAT for angiographic clearance of thrombus burden with more bleeding events in the CDT group.³¹ Kuo and colleagues noted no difference in outcomes and treatment specifics between USAT and CDT in the recently published early results of a multicenter prospective registry.²⁸ Our retrospective analysis of 63 patients suggests that there may be no difference between the two treatment modalities, demonstrating similar rates of outcomes such as survival, hemodynamic stabilization, and echocardiographic parameters in both groups with similar procedure length and lytic dose in the time-adjusted cohorts.³² Selection bias cannot be underestimated in all these studies.

A controlled randomized study will better determine if ultrasound acceleration adds any benefits in the outcomes and costs of catheter directed thrombolysis for patients with acute submassive PE.

d. APPROACH

The study will be designed as a randomized controlled trial comparing standard catheter directed thrombolysis to ultrasound accelerated thrombolysis for the treatment of acute submassive PE.

The study will include patients eligible for catheter directed thrombolysis per the study protocol for submassive PE (CT or echocardiographic RV strain (defined as RV/LV ratio >1) without persisting hypotension <90mmHg or drop of systolic blood pressure by at least 40mm Hg for at least 15 minutes with signs of end-organ hypoperfusion (cold extremities or low urinary output <30 mL/h or mental confusion) and without the need of catecholamine support or cardiopulmonary resuscitation).

The treatment with CDT or USAT are standard of care for submassive PE. All the procedures, tests and follow up visits are according to current standard of care.

Exclusion criteria: age <18; pregnancy; index PE symptom duration >14 days; high bleeding risk (any prior intracranial hemorrhage, known structural intracranial cerebrovascular disease or neoplasm, ischemic stroke within 3 months, suspected aortic dissection, active bleeding or bleeding diathesis, recent spinal or cranial/brain surgery, recent closed-head or facial trauma with bony fracture or brain injury); participation in any other investigational drug or device study; life expectancy <90 days; and inability to comply with study assessments.

At baseline all patients need to have

- 1. Chest CT angiogram with contrast diagnostic of PE

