- 2. Baseline transthoracic echocardiogram
- 3. Baseline cardiac biomarkers
 - a. Cardiac troponin (cTn)
 - b. Brain Natriuretic Peptide (BNP) and/or N-terminal pro-BNP (NT-proBNP)

All patients will be treated initially with unfractionated heparin by using a standardized dosing protocol. Immediately after consent, vital signs will be recorded, a pulse oximetry reading will be obtained with the patient breathing room air for 2 min.

All eligible patients will undergo catheter-directed thrombolysis randomized to either a standard commercially available multi-sidehole catheter or a USAT catheter.

Technical considerations (access, intraoperative tPA bolus, tPA dripping dose etc) will be left to the discretion and preference of the operator. Invasive pressure tracings will be obtained from the drug delivery catheters when positioned in the pulmonary arteries (main, right or left). The maximum tPA dosing should not exceed 24mg.

Termination of lysis will be left to the discretion of the operator. As a general recommendation lysis should be terminated once clinical (e.g. O2 requirements), hemodynamic (e.g. pulse rate or blood pressure) and/or echocardiographic parameters (e.g. RV dilatation) improve or if a complication occurs. Lysis catheters and sheaths can be removed at the bedside. Before removal, invasive pressure tracings will be recorded from the drug delivery catheter.

A transthoracic echocardiogram should be obtained just before or within 24 hours after the termination of lysis.

Within 48h after the termination of lysis patients will get a chest CTA examination.

Patients will be followed up at 3 months and 12 months.

Primary Endpoint: PE thrombus load reduction (CT obstruction index) from baseline to the termination of lysis.

The pre and post lysis CTA will be compared by 2 blinded independent radiologists. For determining the CT obstruction index, the arterial tree of each lung will be considered to have 10 segmental arteries (three to the upper lobes, two to both the middle lobe and the lingula, and five to the lower lobes). The vascular obstruction scores will be determined as previously described by Qanadli et al. and Mastora et al.^{35,36}

Secondary Endpoints:

- 1. Clinical outcomes comparison
 - a. In hospital and 90-day mortality
 - b. Decompensation to massive PE (hypotension <90mmHg and use of catecholamines)

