The study is powered on the primary endpoint that is thrombus load reduction (obstruction index). We propose to compare standard CDT and USAT at post-treatment with analysis of covariance, controlling for differences remaining after randomization. Population parameters for the obstruction score have not been published, so we consulted several relevant studies reporting on thrombus reduction scores in order to predict sample size.^{19,31,34,39} We assumed that CDT with ultrasound enhancement (USAT group) should be \geq 50% more effective than without ultrasound enhancement (control group) and calculated an expected relative mean thrombus reduction of 43% in the CDT control group.^{40,41} We estimated a sample size of 40 per group to detect the differences with a power of 0.80.

REFERENCES

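### The primary ANCOVA ties its covariates to imbalance seen after randomization, so the baseline CT obstruction index is not guaranteed to be in the model

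*Combined protocol and SAP*

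**What the plan says.** The Statistical Analysis part of section d (Approach) holds the only description of the primary model: "We propose to compare standard CDT and USAT at post-treatment with analysis of covariance, controlling for differences remaining after randomization". No covariate is named there or elsewhere, and nothing says how a remaining difference would be identified.

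The natural covariate is already collected. Under "At baseline all patients need to have", the first item is "Chest CT angiogram with contrast diagnostic of PE", and the Schedule of Events also lists the baseline scan. Both scans are read blind: "The pre and post lysis CTA will be compared by 2 blinded independent radiologists".

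On the outcome, the endpoint list gives "Primary Endpoint: PE thrombus load reduction (CT obstruction index) from baseline to the termination of lysis", without saying whether the reduction is absolute or relative. Aim 1 is more specific: "Determine differences in the percentage of thrombus load reduction from baseline to the termination of lysis between the two techniques". The sample-size paragraph works on the same scale, with "an expected relative mean thrombus reduction of 43% in the CDT control group".

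**The concern.** A covariate related to the outcome earns its place in an ANCOVA by removing outcome variance, whether or not the arms happen to differ on it. A model that controls for whatever differences are left after allocation puts the choice on another footing: an analyst following the wording could inspect the baseline table, find the arms similar on the obstruction index, and leave it out. In a trial of 40 per arm the arms will usually look similar, so the variable most likely to sharpen the comparison would usually be dropped.

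The stake is forgone power. That matters somewhat more here because the sample-size paragraph says that no population parameters for the score were available, so 40 per arm rests on uncertain inputs and a margin that costs nothing is worth having.

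**Working it through.** **Inputs from the plan.** 40 per group, power 0.80, control mean reduction 43%, ultrasound arm at least 50% more effective.

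**Assumptions, none of them in the plan.** Two-sided alpha 0.05, normal outcomes, the SD, the correlation ρ between the baseline index and the analysed outcome, and the imbalance rule.

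**1. The plan's own figure.** Reading the effect as 43 × 1.5 = 64.5%, the difference is 64.5 − 43 = 21.5 points. Without an SD or alpha, 40 per group can be neither reproduced nor refuted. Working backwards, a two-sample t-test with 40 per arm has power 0.80 at a standardized effect d = 0.634 (noncentrality 0.634 × √(40/2) ≈ 2.84 on 78 df). The implied SD is 21.5 / 0.634 = 33.9 points. This d is the reference below.

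**2. Baseline always in the model.** Adjustment multiplies the residual SD by √(1 − ρ²) and costs one degree of freedom, plus a small allowance for chance imbalance:

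noncentrality = [d / √(1 − ρ²)] × √(n/2) × √(1 − 1/(2n − 2)), on 2n − 3 = 77 df.

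With n = 40 the last factor is √(1 − 1/78) = 0.9936.

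| ρ | d / √(1 − ρ²) | noncentrality | power |
|---|---|---|---|
| 0 | 0.634 | 2.819 | 0.795 |
| 0.3 | 0.665 | 2.955 | 0.831 |
| 0.5 | 0.732 | 3.255 | 0.895 |
| 0.7 | 0.888 | 3.947 | 0.974 |

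These are the rounded values 0.80 / 0.83 / 0.90 / 0.97. Simulation with 100,000 trials per setting agrees.

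**3. Baseline only when the arms differ.** The plan gives no rule, so one was assumed: adjust if the baseline index differs between arms at p<0.05, otherwise use an unadjusted t-test. Under randomization that rule fires in about 5% of trials, so about 95% are analysed unadjusted.

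| ρ | always adjust | p<0.05 rule |
|---|---|---|
| 0 | 0.80 | 0.80 |
| 0.3 | 0.83 | 0.80 |
| 0.5 | 0.90 | 0.81 |
| 0.7 | 0.97 | 0.82 |

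A looser rule recovers only part of the gain: p<0.20 gives 0.80 / 0.81 / 0.83 / 0.86.

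**4. Type I error.** Under the null the p<0.05 rule rejects in 0.050 of trials at ρ = 0, falling to about 0.036 at ρ = 0.7. With this single covariate and a fixed rule there is no inflation.

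**5. Which correlation matters.** If percentage reduction is analysed, ρ is the correlation of the baseline index with percentage reduction, not with the post-lysis index. The two can differ sharply, because post-lysis index = baseline × (1 − reduction). In a simulation with reduction confined to 0–100%, unrelated to baseline, with means 43% and 64.5%, SD 33.9 points and a baseline coefficient of variation of 0.35, the control-arm correlation between baseline and post-lysis index is 0.49. Power for percentage reduction is nevertheless about 0.79 unadjusted and 0.785 adjusted. A baseline-to-post-lysis correlation near 0.5 can therefore coexist with no gain.

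**The case against.** The best defence is that the plan states ANCOVA without any condition. There is no imbalance test and no threshold, and a fallback to a t-test would contradict the stated method, since ANCOVA needs a covariate in every case. The phrase about remaining differences may only explain what ANCOVA does with chance imbalance, and the baseline index is the obvious covariate. This reading is plausible, and under it no power is lost. It does not remove the need for a change, because the sentence supports either reading and a colleague could not tell from it which model will be fitted. It does mean that the rule in the working is a hypothetical illustration and not the plan's procedure.

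A second defence is that even the unfavourable reading keeps power near the planned 0.80. That is correct: what is lost is an available gain, not planned power.

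A reader might infer three stronger points, none of which the documents support:

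- *That the wording inflates type I error.* The check in the working shows none for one covariate under a fixed rule. Choosing the best of three analyses after seeing results (post score, change score, ANCOVA) would raise it to 0.091–0.101 at correlations of 0.3 to 0.7, but that is a different procedure and nothing in the plan suggests it.
- *That the dependent variable is undefined.* The model sentence does not write it out, but the Summary objectives, Aim 1 and the 43% planning value all point to percentage reduction. The words about post-treatment may refer to timing only, and nowhere is the post-lysis index named as the outcome.
- *That 0.90 or 0.97 power is within reach.* Those values need correlations of 0.5 and 0.7 with percentage reduction, a measure already divided by baseline. The plan offers no evidence on that correlation.

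**Conclusion.** The concern holds as a weakness in how the primary model is specified: the baseline obstruction index is not guaranteed as a covariate, and fitting it in every case is the better method at no cost. The possible benefit runs from nothing at correlation 0 to 0.83 against 0.80 at 0.3, 0.90 against 0.81 at 0.5, and 0.97 against 0.82 at 0.7. The comparison is with one assumed imbalance rule, at 40 per arm, two-sided 0.05 and d = 0.634; alpha, correlations and rule are all assumptions. If the authors always meant to adjust for baseline, the loss is nil and only the sentence needs repair. The trial's validity and its planned 0.80 power are not in question. It should be fixed because it concerns the primary analysis and is cheap to settle.

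**What to change.** Replace the covariate clause in the Statistical Analysis text with wording such as:

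> The primary analysis is an ANCOVA with treatment arm as factor and the baseline CT obstruction index as covariate, fitted in every case. No covariate is added or dropped because of observed imbalance. The dependent variable is the percentage reduction in the obstruction index from the baseline to the post-lysis CT angiogram.

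The dependent variable follows Aim 1 and the sample-size basis, so neither needs restating. As a clarification only, the same place could name which of the two cited obstruction scores enters the model and how the two radiologists' readings are combined.

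The cost is one or two sentences, settled before outcomes are seen by arm. No extra scans or patients are needed, since both CT angiograms are already required.
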